8.1 PRETREATMENT EVALUATION

Baseline evaluations will be performed for ER(-)/PR(-)/AR(+) patients to determine study eligibility. Patients who have received any chemotherapy must have a washout period of 2 weeks before the first dose of study drug is administered. The investigator will document the designated washout period in the patient's source documentation.

The following must be completed within 28 days of initiation of study drug:

[figure not shown]
- Medical history including history of prior therapy
- Medication list (include medications taken within 30 days of baseline visit)
- Physical exam, height and weight.
- Vital signs
- ECOG performance status.
- CBC with differential and platelet count, comprehensive blood panel (including chemistries and liver function tests), tumor markers (Ca15-3 & CEA, or CA 27.29)
- Estradiol, total testosterone, free testosterone, sex-hormone binding globulin,
- Serum pregnancy test (for women of childbearing-potential) will be conducted within 72h of first study drug administration (negative results required for study drug administration).
- CT scan of chest, abdomen and pelvis
- Bone scan or PET scan

9.1 TREATMENT/INTERVENTION PLAN

9.2 Agent Administration

Treatment will be administered on an outpatient basis. Bicalutamide is administered orally at 150 mg (three 50mg tablets) on a continuous daily schedule. A cycle length consists of 4 weeks of therapy. Please refer to the Time and Events Calendar (Section 10) for a detailed description of required tests. Radiographic tumor assessment will take place every 3 cycles.

Expected adverse events for bicalutamide are described in Section 5.0. Appropriate dose modifications for bicalutamide are described in Section 4.2 and Section 11.2. Two 50mg dose reductions are permitted per protocol. A treatment delay of up to 2 weeks is permitted. Therapy will continue until disease progression or unacceptable toxicity.

10.0 EVALUATION DURING TREATMENT/INTERVENTION

Day 0 and every 4 weeks (+/- 5 days), the following clinical and laboratory assessments must be done prior to continuation of treatment with bicalutamide:

- History and physical examination, including:
 - Vital signs
 - ECOG performance status
 - o Weight
 - Concomitant medications
- Laboratory assessments, including: (screening labs can be used as Day 0 labs)
 - CBC with differential and platelet count
 - Comprehensive metabolic panel (Na, K, Cl, CO2, BUN, Creatinine, Ca, Glucose, Total Protein, Albumin, Alkaline Phosphatase, Total Bilirubin, AST and ALT)
- Adverse Event Evaluation (toxicity assessment using the NCI CTC version 3)
- Blood for correlative study of hormonal levels including estradiol, total testosterone, free testosterone, and sex-hormone binding globulin will be performed at baseline, after Cycle #1 and at the end of study. (See further description below)

Every 12 weeks (+/- two weeks), tumor assessments will be performed. Patients with measurable disease will be evaluated for complete response (CR), partial response (PR), stable disease (SD) or progressive disease (PD) using RECIST criteria, using the same modality of imaging performed at baseline. Patients with non-measurable disease will be evaluated for either stable disease or progressive disease. Responders and stable disease patients will continue on study unless they develop unacceptable toxicity. Progressive disease or unacceptable toxicity (after a maximum of two dose reductions) will be the criteria for treatment failure and discontinuation from the study.

Response assessment will include:

- Radiologic scans of disease sites (e.g. CT scan of chest, abdomen and pelvis and PET or bone scan if there are bone lesions identified on pre-study bone imaging)
- Measurement of all target lesions that are followed by physical examination
- Patients achieving a CR or PR must have confirmation of response at least 4 weeks following the initial response determination.
- End-of-Study (EOS) Evaluation: At the time patients are removed from study, laboratory and clinical evaluations to assess adverse events (AEs) will be performed. Serum hormone panel including estradiol, free and total testosterone and serum hormone binding globulin will be collected. Radiologic studies for antitumor response will be repeated if they have not been performed within the previous 28 days.
- Adverse Event Resolution Follow-up: Any AE that started anytime beginning from the

IRB#: 07-022A(13)

time the patient has registered, and up to 30 days after the last dose of bicalutamide, must be followed until the AE has resolved or stabilized.

Correlative study methods:

All correlative studies will be performed for the purpose of exploratory analysis. Correlative study will include immunohistochemical (IHC) analysis of proteins representing the ER(-) Class A and Basal subtypes, including ALCAM, SPDEF and CK 5/6. IHC analysis will be performed using preexisting formalin fixed paraffin embedded biopsy or excision tissue from cancer sites. An exploratory analysis will be performed to correlate IHC expression profile and response to bicalutamide. In addition, the effect of bicalutamide administration on serum hormone level will be investigated. Estradiol, free and total testosterone and serum hormone binding globulin will be measured at baseline, after cycle #1 and at the end of study to describe changes in these circulating hormones in response to androgen blockade in women.

Paraffin embedded tissue from primary tumor or metastatic site which has tested AR+ will be requested from participating patients. These tumor blocks, if available, will be collected and stored for the purpose of future correlative studies to understand the biology of AR+ breast cancer.

IRB#: 07-022A(13)

Time and Events Schedule

Study Parameter	Prestudy	Every cycle ^a	Every 3 cycles	Study Termination (EOS)	AE resolution
Informed consent ^b	X				
History	Х				
Concomitant medications	Х	Х		Х	
Physical examination	Х	Х		Х	Х
Vital signs	Х	Х		Х	Х
Height and body weight	Х	Xc		Xc	
ECOG performance status	Х	Х		Х	Х
Adverse Event Evaluation		Х		Х	
Disease Status					
Tumor assessment (clinical)		\mathbf{V}^{d}			
Tumor assessment with CT scan	Х		Xe	Х	
Tumor assessment with PET or Bone scan ^g	Х		Х	Х	
Toxicity assessment (by patient and by physician)		Х		Х	
CBC with differential and platelet count	Х	Х		Х	
Comprehensive blood panel (including chemistries and liver function tests) ^h	X	Х		Х	X
Tumor Markers (Ca 15-3 & CEA, or CA 27- 29)	Х	Х		Х	
Estradiol, total testosterone, free testosterone, sex-hormone binding globulin *Only after Cycle #1.	Х	X*		Х	
Pregnancy test	Xf				

^a one cycle is equal to 4 weeks

^b after study consent form has been signed, pathological testing of tumor for androgen receptor (AR) status will be performed. If patient's tumor is AR+ then they will be eligible to participate in the therapeutic study. If AR- they will not be permitted to participate in study.

- ^c body weight only
- ^d by physical exam
- ^e confirm response 28 days
- ^f females of childbearing potential only, within 72 hours of drug initiation

^g bone scan or PET must be repeated if bone disease is known from baseline scans. If patient does not have bone disease, follow-up bone or PET scans are at the discretion of the treating physician. If PET/CT scans are being performed and can monitor for bone lesions, then no further bone scans are necessary.

* after Cycle 1

^h Comprehensive blood panel may include the following: Na, K, Cl, CO2, BUN, Creatinine, Ca, Glucose, Total Protein, Albumin, Alkaline Phosphatase, Total Bilirubin, AST and ALT

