6.1 CRITERIA FOR SUBJECT ELIGIBILITY

6.2 Subject Inclusion Criteria

A patient will be eligible for androgen receptor expression testing if the following criteria are met:

- Pathologically confirmed adenocarcinoma of the breast which is ER(-) and PR(-).
- Non-measurable or Measurable, metastatic disease

IRB#: 07-022A(13)

A patient will be eligible for participation in the therapeutic trial if the following criteria are met:

- Androgen receptor expression testing confirms that the patient's tumor is ER(-)/PR(-) /AR(+). ER, PR and AR are considered positive if greater than 10% of cell nuclei are immunoreactive. Receptor testing may be performed on either primary tumor specimen or tissue from a metastatic site.
- Prior neo-adjuvant or adjuvant chemotherapy is allowed. Any number of chemotherapy regimens are allowed for metastatic disease. There is no restriction on prior treatment with hormonal agents.
- Prior treatment with trastuzumab must have been given if patient has Her2/neu positive disease (defined as IHC=3+ or FISH amplified).
- At least 2 weeks since prior cytotoxic chemotherapy. Patients should have recovered from all acute effects of such therapy.
- Absence of active brain metastatic disease or leptomeningeal disease. If patient has a history of brain metastases, lesions must be stable for at least 3 months (as documented by either head CT or brain MRI).
- At least 4 weeks from major surgery with full recovery
- ECOG performance status 0-1
- Age 18 years or greater
- Laboratory parameters as follows:
 - \circ ANC $\geq 1.5 \times 10^9$ cells/L
 - \circ Platelets $\geq 100 \text{ x } 10^9 \text{ cells/L}$
 - $\circ \quad Hgb \geq 9g/dL$
 - AST (SGOT), ALT (SGPT) ≤ 2.5 x upper limit of normal range (ULN); total bilirubin ≤ 1.5 x ULN; alkaline phosphatase ≤ 2.5 x ULN (unless bone metastases are present in the absence of liver metastases), creatinine ≤ 1.5 mg/dL
- If female of childbearing potential, pregnancy test is negative
- If fertile, the patient agrees to use an effective method to avoid pregnancy for the duration of the study
- Informed consent has been obtained

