11.2.1 Adverse event

An adverse event is the development of an undesirable medical condition or the deterioration of a pre-existing medical condition following or during exposure to a pharmaceutical product, whether or not considered causally related to the product. An undesirable medical condition can be symptoms (*eg*, nausea, chest pain), signs (*eg*, tachycardia, enlarged liver) or the abnormal results of an investigation (*eg*, laboratory findings, electrocardiogram). In clinical studies, an AE can include an undesirable medical condition occurring at any time, including run-in or washout periods, even if no study treatment has been administered. In cancer clinical trials, many AEs are in fact related to progression of the patient's underlying malignancy.

An adverse event includes:

- An exacerbation of a pre-existing illness;
- An increase in frequency or intensity of a pre-existing episodic event or condition;
- A condition detected or diagnosed after study drug administration even though it may have been present prior to the start of the study;
- Continuously persistent disease or symptoms that were present at baseline and worsen following the start of the study.

IRB#: 07-022A(13)

An adverse event does not include:

- Medical or surgical procedures (eg, surgery, endoscopy, tooth extraction, or transfusion); however, the condition that leads to the procedure is an adverse event (Procedures that occur during the trial should be recorded on the Concurrent Procedure CRF);
- Pre-existing diseases, conditions or laboratory abnormalities present or detected at the start of the study that do not worsen;
- Hospitalizations or procedures that are done for elective purposes not related to an untoward medical occurrence (eg, hospitalizations for cosmetic or elective surgery or social/convenience admissions);
- The disease being studied or signs/symptoms associated with the disease unless more severe than expected for the patient's condition;
- Overdose of study drug without any clinical signs or symptoms.

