11.3.4 Abnormal Hepatic Function

Bicalutamide should only be administered if hepatic function is within the parameters established in the eligibility criteria. Hepatic toxicity from bicalutamide may occur but it is uncommon. Therefore, hepatic dysfunction that occurs while the patient is on study should prompt an evaluation to determine the cause, including the possibility of progressive metastatic disease and hepatotoxicity from concurrent medications. A maximum of 2 weeks will be permitted for liver enzymes to return to within normal range for the institution.

If transaminases (ALT/AST) are elevated > 2.5x normal levels, treatment should be withheld until levels fall to ≤ 2.5 x normal levels. If total bilirubin is elevated > 1.5 x normal level, treatment should be withheld until level falls to ≤ 1.5 x normal levels. If alkaline phosphatase is elevated > 2.5 x normal value, treatment should be withheld until levels fall to ≤ 2.5 x normal level (unless bone metastases are present in the absence of liver metastases). A dose reduction should then be administered following resolution of any or all of these liver enzyme abnormalities.

If transaminases are subsequently elevated > 2.5 x normal; or, if total bilirubin is elevated > 1.5 x normal value, or if alkaline phosphatase is elevated > 2.5 x normal value (unless bone metastases are present in the absence of liver metastases), treatment will again be withheld until AST/ALT decrease to \leq 2.5 x normal, total bilirubin decreases to \leq 1.5 x normal value and alkaline phosphatase decreases to \leq 2.5 x normal value. A second dose reduction should then be administered.

If, after 2 dose reductions, AST, ALT, total bilirubin and/or alkaline phosphatase remain elevated, patient should be taken off study, and laboratory abnormalities should be reported as an unacceptable toxicity.

[figure not shown]

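### Screening labs up to 28 days old may replace the Day 0 panel while chemotherapy is allowed until day -14, so the only pre-dose labs can predate the last chemotherapy dose

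*Combined protocol and SAP*

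**What the plan says.** Four sets of provisions bear on this point.

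- **Age of screening labs.** Section 8.1 heads its list of baseline tests, which includes the CBC, chemistries and liver function tests, with "The following must be completed within 28 days of initiation of study drug".
- **Day 0 labs.** Section 10.0 sets clinical and laboratory assessments at "Day 0 and every 4 weeks (+/- 5 days"), and attaches to the laboratory item the allowance that "screening labs can be used as Day 0 labs". The allowance has no shorter window and no link to the last chemotherapy dose. History, physical examination and adverse event evaluation at Day 0 are not waived.
- **Chemotherapy interval.** Section 8.1: "Patients who have received any chemotherapy must have a washout period of 2 weeks before the first dose of study drug is administered". Section 6.2: "At least 2 weeks since prior cytotoxic chemotherapy. Patients should have recovered from all acute effects of such therapy".
- **Hepatic condition for dosing.** Section 11.3.4: "Bicalutamide should only be administered if hepatic function is within the parameters established in the eligibility criteria". It gives no date for the test that shows this at first dose.

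On the safety side, section 11.2.1 counts as an adverse event "A condition detected or diagnosed after study drug administration even though it may have been present prior to the start of the study", and excludes "Pre-existing diseases, conditions or laboratory abnormalities present or detected at the start of the study that do not worsen". Section 17.2.1 records clinically significant baseline laboratory abnormalities as pre-treatment findings and presents grade 3 or 4 chemistry values that occur after first dose. Section 17.2.5 defines treatment-emergent events by onset or worsening after study drug starts. It summarises all events regardless of cause and, separately, those judged at least possibly related.

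**The concern.** Sections 6.2 and 11.3.4 state what should be true when bicalutamide starts, but the visit schedule does not guarantee a laboratory result that shows it. The one panel that would do so, at Day 0, can be replaced by a panel drawn before the last chemotherapy dose. The history and physical examination that remain at Day 0 cannot show transaminases, bilirubin or blood counts.

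Two things are at stake. The first is patient safety: a patient whose liver tests have moved outside the entry limits can start without anyone knowing. The second is the safety baseline. Safety is a secondary objective, section 5.1 notes that the drug has not been tested in women at these doses, and the insert in Appendix A warns of liver injury, generally in the first three to four months. Separating drug effect from carry-over therefore depends on a hepatic baseline taken after the previous therapy.

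The adverse event definitions make the baseline matter. An abnormality detected at the start that does not worsen is excluded. The same abnormality first detected after dosing is counted.

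**Working it through.** **The plan's own calculation.** The only design figure is in section 14.0: at least 4 of 28 patients, 5% versus 20%, with Type I error 5% and Type II error 16%. The exact binomial tails are P(X >= 4 | n = 28, p = 0.05) = 0.0491 and P(X >= 4 | n = 28, p = 0.20) = 0.8398, so Type II error = 1 - 0.8398 = 0.1602. The stated figures are reproduced. Nothing below enters them.

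**Inputs for the timing check**

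| Input | Value | Source |
|---|---|---|
| Oldest permitted screening labs | day -28 | 8.1 |
| Latest permitted chemotherapy | day -14 | 6.2, 8.1 |
| Screening labs reused at Day 0 | allowed | 10.0 |
| Next scheduled panel | 4 weeks +/- 5 days | 10.0 |
| Patients | 28 | 14.0 |

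**Timing**

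1. Labs before the last chemotherapy dose: up to 28 - 14 = 14 days. The extreme is not needed. Any panel drawn from day -28 up to a last dose on day -14 meets the timing rules and says nothing about that dose's effect.
2. Next scheduled panel: day 28 - 5 = 23 to day 28 + 5 = 33.
3. Longest gap between panels: 28 + 33 = 61 days. With a Day 0 panel the longest gap would be 33 days, so the waiver adds up to 28.
4. Time from day -14 chemotherapy to the next scheduled panel: 14 + 23 = 37 to 14 + 33 = 47 days. A carried-over abnormality must last that long, or be found at an unscheduled test, to be recorded at all.

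**How such a finding is recorded.** Suppose liver tests are normal at day -28, chemotherapy follows at day -14, and the tests are abnormal at day 23 to 33.

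- Under 11.2.1 it is an adverse event even if it was present before the first dose. With no post-chemotherapy baseline, its onset appears to fall after study drug (17.2.5).
- It enters the all-causality table (17.2.5) and, if grade 3 or 4, the chemistry presentation (17.2.1). Neither has a causality filter.
- It enters the treatment-related table only if judged at least possibly related (17.2.5).
- If it exceeds the 11.3.4 limits, that section calls for an evaluation of cause, a hold and then a dose reduction. It does not exempt abnormalities with another cause from the hold and reduction.

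**Effect on percentages.** One patient in 28 is 1/28 = 3.6 percentage points. For the toxicity tables, one recorded abnormality is enough. For the tolerability percentage in 14.0 it is not, because that measure allows up to two reductions. The patient must come off treatment, for example through failure to resolve within two weeks. If the abnormality dates from day -14 chemotherapy, that is 37 + 14 = 51 to 47 + 14 = 61 days after it.

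**Frequency.** The documents give no rate. Taking an assumed proportion q of patients with such an abnormality, the expected number is 28q and the chance of at least one is 1 - (1 - q)^28:

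| Assumed q | Expected number | Chance of at least one |
|---|---|---|
| 2% | 0.6 | 43% |
| 5% | 1.4 | 76% |
| 10% | 2.8 | 95% |
| 20% | 5.6 | 99.8% |

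These values show a range and are not estimates.

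**The case against.** The strongest reply is that the rules in 6.2 and 11.3.4 are in force whatever section 10.0 allows. A patient who has not recovered, or whose liver tests are out of range, should not be dosed, and permission to reuse labs does not override that. Known or symptomatic toxicity would be picked up at the Day 0 examination and given an onset before study drug. The sequence is also unusual: patients join when their physician decides to change therapy (1.3), and concurrent chemotherapy is excluded (6.3), so eligibility labs would have to be followed by a further chemotherapy dose.

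Much of this stands. The rules are not overridden; their verification is undated. Only a silent, untested abnormality escapes, and how often that happens is unknown. But the documents do not forbid the sequence, and a silent abnormality is the kind that only a blood test detects.

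Three stronger readings are tempting and are not supported.

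- **That chemotherapy toxicity will be recorded as bicalutamide's.** Section 11.1 requires an immediate effort to establish etiology, 11.3.4 requires an evaluation of the cause of hepatic dysfunction, and 17.2.5 keeps treatment-related events in a separate summary. Misattribution is possible, not built in.
- **That the tolerability percentage is biased by each such case.** One hold and one reduction do not make a patient intolerant under 14.0.
- **That the marrow criteria raise an equal problem.** A transient nadir would probably be missed at week 4, the withdrawal criterion in 4.3 after two reductions is non-hematologic, and 11.3.5 exempts anemia from its grade 3 hold. The hepatic case carries the point.

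Nor is the 33 days on drug before the next scheduled panel caused by the waiver. It is the ordinary visit interval with its window.

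**Conclusion.** The gap is real and narrow. On the current text the only laboratory results before first dose can predate the last chemotherapy by up to 14 days, and the next scheduled panel can be up to 61 days after them. In that case no laboratory test verifies the recovery condition in 6.2 or the hepatic condition in 11.3.4 before dosing.

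A persisting hepatic abnormality can then be counted as treatment-emergent, may be attributed to bicalutamide, and can lead to a hold and reduction. Each such patient moves a toxicity percentage by 3.6 points. The tolerability percentage falls by the same amount only for a patient who comes off treatment as a result.

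This rests on three assumptions: the patient receives chemotherapy after the screening panel, the abnormality is silent at Day 0, and it lasts to about week 4 or is found earlier at an unscheduled test. The primary endpoint, the sample size and the error rates are unaffected. The change is worth making because it protects patients and the safety baseline at little cost, not because the trial's main conclusion is at risk.

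**What to change.** Reconcile sections 8.1 and 10.0 with sections 6.2 and 11.3.4 by limiting the waiver in section 10.0. Suggested content: screening CBC and metabolic panel may serve as the Day 0 labs only if drawn after the last dose of prior cytotoxic chemotherapy. Otherwise the Day 0 panel already on the schedule is drawn and checked against the existing limits in 6.2. Name the panel used in this way as the baseline for grading treatment-emergent laboratory abnormalities in 17.2.1 and 17.2.5.

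Whether to set a tighter window in days is for the sponsor to choose; nothing in this point requires one.

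The cost is one sentence in section 10.0, a short addition to the safety analysis text, at most one blood draw that the schedule already lists for recently treated patients, and an occasional short delay in starting. Patients without chemotherapy after their screening labs are not affected.
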